10.1.2.1.2 Unexpected Adverse Reactions

Unexpected Adverse Reaction Definition

An unexpected adverse reaction is any untoward and unintended response that is related to the administration of the study drug at any dose that is not consistent with the applicable product information (e.g. investigators brochure for an unauthorized investigational medicinal product or summary of product characteristics for an authorized product).

All suspected unexpected serious adverse reactions (SUSARs) will be the subject of expedited reporting. The sponsor/CRO shall ensure that all relevant information about a SUSAR that is fatal or life-threatening is reported to the relevant competent authorities and IEC/IRB within 7 days after knowledge by the sponsor of such a case and that relevant follow up information is communicated within an additional 8 days. All other SUSARs will be reported to the relevant competent authorities and IEC/IRB within 15 days after knowledge by the sponsor of such a case. All investigators should follow up SUSARs until the event is resolved or until, in the opinion of the investigator, the event is stabilized or determined to be chronic. Post study SUSARs that occur after the subject has completed the clinical study must be reported by the investigator to the sponsor.

Warnings and Precautions

Safety Assessment to Exclude Obstructive Sleep Apnea

Sodium oxybate, when given to subjects with obstructive sleep apnea (OSA) will increase the risk of advancing sedation and respiratory depression. To support screening activities in ensuring subjects with OSA are detected and excluded as early as possible from the FT218 clinical study, a number of primary criteria will be assessed at Visit 1 to rule out OSA. Specifically, this will include taking the subject's neck circumference and documenting snoring patterns. These criteria will be assessed relative to ESS score, BMI, BP, age, and gender. A determination on eligibility to proceed through the screening period will be made relative to OSA risk. PIs will be trained on this at Site Initiation. In the event that following completion of the assessment the risk of OSA goes undetected, confirmation of the presence of OSA will be detected on overnight PSG (AHI \geq 15) at Week 3 in the screening and baseline period of the study. Where OSA is detected, the

subject will be withdrawn from study. Include any information relevant to safety (i.e., known side effects or treatment of potential side effects).

Safety Assessment of Suicidality

Study subjects will be assessed at study screening for suicidality using the C-SSRS. At risk subjects will be withdrawn. Risk for the emergence of suicidality, using the C-SSRS, will be assessed at each study visit for the duration of the clinical study. Where risk is identified, study subjects will immediately be withdrawn from study. The PI will implement the most appropriate medical and psychological care pathway to ensure subject safety and recover. Where a subject is withdrawn for suicidality this will be clearly indicated as the reason for withdrawal on the withdrawal form and in source data.

Safety Assessment for Abuse and Dependence

Subjects with a history of drug abuse and/or dependence will be assessed at the screening visit by the PI/designee. Subjects with a known and discernable history of abuse and/or dependence will be excluded.

Subjects will be assessed by the PI/designee for any signs and symptoms which may indicate an emergent abuse and dependence i.e. positive urine drug screen indicating concomitant use of contraindicated prescription drugs and/or illicit drug use, evidence or family report of concomitant use of alcohol with study drug product, suspicious claim(s) of lost product and looking for replacement study drug

10.1.2.2 Clinical Laboratory Evaluation

The hematology and biochemistry laboratory analyses will be performed at a central laboratory (ACM Global Central Laboratory, Rochester, US). Reference ranges will be supplied and used by the investigator to assess the laboratory data for clinical significance and pathological changes. The following laboratory safety tests will be performed:

Hematology

Hemoglobin, hematocrit, white blood cell count (total and differential), red blood cell count, platelet count, mean cell volume, mean cell hemoglobin, and mean cell hemoglobin concentration

Biochemistry

Creatinine, blood urea nitrogen, aspartate transferase, alanine transferase, gamma glutamyltransferase, alkaline phosphatase, total bilirubin, albumin, globulin, total protein, sodium, potassium, chloride, bicarbonate, estimated glomerular filtration rate, carbon dioxide, glucose, total cholesterol, triglycerides, and creatine phosphokinase.

Urinalysis

pH, glucose, ketones, blood, and protein by dipstick test at the central laboratory. If any of these parameters gives a positive result, a quantitative result will be transmitted.

10.1.2.2.1 Other Laboratory Variables

Drugs of Abuse Screening: Urine drug screen will comprise cocaine, benzodiazepines, cannabis, opiates, and barbiturates.

Serology: Hepatitis B surface antigen, and hepatitis C antibody

Pregnancy: serum β -human chorionic gonadotropin test will be performed at screening (Visit 1), urine β - human chorionic gonadotropin test at all other visits.

10.1.2.3 Vital Signs

Vital signs consisting of systolic and diastolic BP and heart rate will be recorded after at least 5 minutes in the sitting position.

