Efficacy assessments include MWT, CGI, Sleep and Symptom Daily Diary, nocturnal PSG, and ESS

Safety:

Safety assessments include AEs, laboratory parameters, vital signs, physical examination, 12-lead electrocardiogram, Columbia-Suicide Severity Rating Scale

Statistical Analysis:

A mixed-effects means model with repeated measures (MMRM) will be used to analyze change from baseline for each of the coprimary endpoints. Each model will include treatment, time, treatment-by time interaction, site and baseline score as fixed effects and subjects as random effects. [REDACTED]

The primary hypothesis tests of the efficacy of individual doses will be performed as contrasts within the mixed models. The hypothesis testing will proceed in the following order: first, to test hypotheses for EDS, both MWT and CGI will be examined for statistical significance for the 9.0 g dose using the data collected during Periods 3c(i), and 3c(ii). If both tests are significant, NCA for the same dose will be tested. If the first test fails (either MWT or CGI not significant), the data for the 9.0 g dose was not able to reject the null hypothesis of equality to placebo for either symptom. If the first test is significant (both MWT and CGI significant) but the second test (NCA) fails, the dose has been demonstrated to exceed placebo for EDS treatment but not for cataplexy. If both tests are statistically significant, the dose has been shown to be effective for EDS and cataplexy.

If the 9.0 g dose demonstrates efficacy for both EDS and cataplexy, the same sequence of testing will be followed for the 7.5 g dose using the data collected during Periods 3b(i) and 3b(ii). If the 7.5 g dose demonstrates efficacy for both EDS and cataplexy, the same sequence of testing will be followed for the 6 g dose using the data collected during Period 3a.

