6.6 Potential Risks and Benefits

Based on early studies of FT218, it is possible to predict some of the discomforts and risks. The data suggest that the potential risks of FT218 are likely to be manageable and will be monitored like Xyrem. Clinical studies with Xyrem have yielded detailed information of its safety profile. Xyrem is approved by the FDA in the US and EMA for the treatment of subjects with narcolepsy. The potential risks of FT218 from PK studies in humans have been discussed in the

summary from the Phase 1 safety study (discussed in [Section 6.3](#)) and to date are consistent with and similar to what has been previously reported with sodium oxybate.

Clinical safety of Xyrem has been established and forms the basis for the FT218 safety plan. All causality and treatment-related events for Xyrem include: abdominal pain, diarrhoea, nausea, vomiting, fatigue, peripheral oedema, anorexia, dizziness, headache, abnormal dreams, confused state, nightmare, sleep walking and enuresis. The most commonly identified AEs for sodium oxybate are nausea, dizziness and headache. In terms of AEs where there was a dose response relationship, these AEs included nausea, vomiting, paraesthesia, disorientation, irritability, disturbance in attention, feeling drunk, sleepwalking and enuresis. These events are most pronounced at the higher, 9.0 g dose, and in some cases related to the 7.5 g dose. The up-titration methods, as used with Xyrem, to maximum dose, are thus appropriate to establish safety and tolerability in study subjects who will participate in this clinical study.

The safety profile of Xyrem is thus well characterized. The safety profile, as described in the Xyrem approved labelling supports the safety of the FT218 study formulation. In addition, all necessary precautions and warnings related to subject self-care and self-monitoring for any signs and symptoms of respiratory or CNS depression, alcohol consumption, contraindicated medications, driving and use of heavy machinery apply to FT218. The proprietary extended-release oral suspension technology used for FT218 is well established. The technology is the same as that used for the marketed product Coreg CR (carvedilol, NDA 022012) for the treatment of hypertension, left ventricular dysfunction and mild to severe heart failure. This has been marketed in the US since 2007.

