8.3.3 Exclusion Criteria

Subjects will be excluded from the study if one or more of the following criteria are applicable:

1. Prior use of sodium oxybate is allowed in the study but with the following exclusions:
 - a. Previous dosing must have been limited to no more than 4.5g per night
 - b. Patient should not have taken sodium oxybate for more than 2 weeks

- c. All previous dosing must not have occurred within the last year prior to entry to the study
2. Current use of sodium valproate
3. Any use of the following prohibited medications for the duration of the clinical study: (Section 8.4.8.1)
 - a. Anticonvulsants
 - b. Clonidine
 - c. SSRIs and serotonin and norepinephrine re-uptake inhibitors (SNRIs)
 - d. MAOIs
 - e. TCAs
 - f. Hypnotics
 - g. Anxiolytics
 - h. Sedating antihistamines
 - i. Antipsychotics
 - j. Other experimental medications designed to treat narcolepsy, cataplexy or any other condition
4. Treatment with any investigational products within 3 months before study enrollment
5. Any drug known to affect sleep-wake function. Concomitant stimulant use is permitted (Section 8.4.8)
6. A diagnosis of sleep apnea or any other sleep disorder known to cause EDS as determined by PSG and sleep history, including any PSG results indicating an apnea-hypopnea index (AHI) ≥ 15
7. The presence of any unstable or clinically significant medical and psychiatric disorders (as determined by medical or psychiatric history, physical examination, and/or clinical laboratory test) which in the opinion of the investigator may either put the subject at risk by participation in the study, or may influence the results of the study
8. Subjects with a previous history or current ideation of suicide attempt
9. Subjects who have a history of drug or alcohol use that, in the opinion of the investigator would interfere with study subject safety and adherence to study requirements
10. Required commercial or equivalent driving during the study period
11. An occupation that requires variable shift work or routine night shifts
12. Any travel across more than 3 time zones during the course of the study
13. Consuming more than 14 standard alcoholic drinks per week, on average, before participating in the clinical research study
14. Smoking during the night (approximately between 9 pm and 7 am) during the course of the study

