10.1.2.4 Physical Examination

A complete physical examination including weight and evaluation of main body systems/regions, including: skin and mucous, ears/nose/throat, pulmonary, cardiac, GI, and neurological systems.

In case of abnormality, a comment will be recorded in the eCRF and subjects medical notes. Any deterioration in condition will be reported as an AE.

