2.6.3 ENDPOINTS FOR SAFETY

Safety will be evaluated based on reports of adverse events either spontaneously reported or observed in clinical laboratory analyses. All adverse events and all serious adverse events will be tabulated by system organ class and preferred term.

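### Respiratory depression is a named risk, but no readable safety outcome measures breathing during sleep, although overnight PSGs follow dosing at 6.0, 7.5 and 9.0 g

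*Protocol*

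**What the plan says.** **The risk.** Protocol 6.6 carries over to FT218 the precautions on self-monitoring for "signs and symptoms of respiratory or CNS depression". Exclusion 19 in Protocol 8.3.3 keeps out subjects whose other conditions would raise that risk. The warnings under Protocol 10.1.2.1.2 state: "Sodium oxybate, when given to subjects with obstructive sleep apnea (OSA) will increase the risk of advancing sedation and respiratory depression".

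**The safety measurements.** The Protocol synopsis gives the list: "Safety assessments include AEs, laboratory parameters, vital signs, physical examination, 12-lead electrocardiogram, Columbia-Suicide Severity Rating Scale". Protocol 10.1.2.3 defines vital signs: "Vital signs consisting of systolic and diastolic BP and heart rate will be recorded after at least 5 minutes in the sitting position". The physical examination in Protocol 10.1.2.4 covers "skin and mucous, ears/nose/throat, pulmonary, cardiac, GI, and neurological systems".

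**The safety analysis.** SAP 2.6.3 says: "Safety will be evaluated based on reports of adverse events either spontaneously reported or observed in clinical laboratory analyses". Protocol 11.10 uses the same basis. Protocol 11.10.1.1 and the readable part of SAP 4.7 add laboratory summaries and, in the SAP, exposure.

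**The sleep recordings.** Protocol Appendix 17.2 and sections 9.2.2, 9.2.4 and 9.2.6 place an overnight PSG at Visits 4, 6 and 8, with that night's dose dispensed at the clinic beforehand. The synopsis lists nocturnal PSG among the efficacy assessments. AHI appears only as an entry criterion: exclusion 6 in Protocol 8.3.3 ("including any PSG results indicating an apnea-hypopnea index (AHI) ≥ 15"), the historical PSG in 9.1.1, and the baseline PSG in 10.1.2.1.2.

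**The concern.** The drug is taken at bedtime, so an effect on breathing would occur while the subject sleeps, mostly at home. A sleeping subject is poorly placed to notice or report a subclinical change. The safety objective is relative safety against placebo (Protocol 7.3), and SAP 2.1.3 sets it dose by dose. If no breathing variable is defined, the trial may give no systematic between-arm comparison on a risk for which it screens subjects at entry. This matters most at 9.0 g: the healthy-volunteer support described in Protocol 6.5 and SAP 1.1 covers FT218 at 4.5, 6.0 and 7.5 g.

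**Working it through.** The plan gives no figure to reproduce here. The check sets each listed safety measurement against the question, and then counts the recordings.

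| Measurement | Timing (Protocol) | Breathing during sleep? |
|---|---|---|
| Adverse events | All visits, volunteered or elicited (10.1.2.1) | Only if an event is noticed or a finding reaches the site |
| Laboratory tests | Visits 1, 2 and 8; Visit 9 if indicated | No |
| Vital signs | Visits 1 to 8, seated; BP and heart rate (10.1.2.3) | No |
| Physical examination | Full at Visits 1 and 8; otherwise at the PI's judgement | No; a clinic examination, though it includes the pulmonary system |
| ECG | Visits 1 and 8 | No |
| C-SSRS | Visits 1 to 8 | No |

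**Dosing nights (Appendix 17.2).**
- Total: 13 weeks × 7 = 91.
- Self-administered without PSG: 10 weeks × 7 + 3 weeks × 6 = 88.
- Dispensed at the clinic before PSG: 91 − 88 = 3, or 3/91 = 3.3%.
- These are night 7 of Weeks 3, 8 and 13, that is, one each at 6.0, 7.5 and 9.0 g or matching placebo. None is at 4.5 g, and none falls on the first night of a dose step.

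**Is AHI obtainable?** The baseline PSG must yield an AHI, because a value of 15 or above excludes the subject. The on-treatment PSGs therefore probably carry the same channels. This is an inference: the readable text does not give the on-treatment montage, and Protocol 11.12 describes the central laboratory's task only for Visit 2.

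**Is AHI used on treatment?** No readable section says that AHI or oxygen saturation at Visits 4, 6 or 8 is scored, returned to the site, compared by arm or sent to the DSMB.

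**Does the adverse event route fill the gap?** In part. Protocol 10.1.2.1 allows abnormal test findings to be adverse events. The same section, however, sends excessive daytime sleepiness, disturbed nocturnal sleep, nightly arousals and sleep quality to the efficacy data and not to adverse events. Exclusion 6 itself treats sleep apnea as a cause of daytime sleepiness, so some symptoms through which disturbed breathing might show are removed from adverse event capture.

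**The case against.** **Redaction.** This is the strongest objection. The protocol section between 10.1.1.3 and 10.1.1.5, the secondary and exploratory endpoints, and nearly all of the SAP after the readable part of 4.7 are blacked out or missing. It stands: absence from the whole plan cannot be shown. It does not remove the point, because Protocol 10.1.2, Protocol 11.10 and SAP 2.6.3, where a safety variable would be expected, are readable and contain none.

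**Other detection routes.** A reader might infer that the trial cannot detect breathing effects at all, or that the recordings go unused. The documents do not support that. An overt event or an abnormal PSG finding can be reported as an adverse event, adverse events are tabulated by arm against placebo, and a DSMB reviews safety (Protocol 11.11). Eligibility is also re-confirmed at Visits 4 to 8, although nothing says that AHI is re-read then. What is missing from the readable text is a systematic measure.

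**Scope of the risk.** The warning in 10.1.2.1.2 concerns subjects with obstructive sleep apnea, whom the protocol excludes. Protocol 6.3 concerns combination with other CNS depressants, and also reports that the respiratory center keeps its sensitivity to carbon dioxide. Only 6.6 extends the risk to subjects generally, as a precaution, and its adverse event lists name no respiratory event. This limits the urgency. It does not explain why subjects with an AHI below 15 would have no follow-up value reported.

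**What AHI measures.** AHI counts apneas and hypopneas and may miss sustained hypoventilation. That is correct, and is why oxygen saturation should be added if it is recorded.

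**Conclusion.** The point holds for the readable text. Respiratory depression is a named risk, no readable safety assessment or analysis systematically measures breathing during sleep, and three post-dose overnight PSGs in each completing subject have no stated respiratory safety use. Subclinical effects would surface only through unsystematic adverse event reports.

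The conclusion assumes that the redacted text does not already define such a variable. The remedy also depends on the respiratory channels being recorded on treatment. No precision can be claimed for an AHI comparison, because the readable documents give neither a sample size nor a standard deviation for AHI. This is an inexpensive improvement to the safety plan. It is not an error in the efficacy analysis, and no power or alpha figure depends on it.

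**What to change.** In Protocol 10.1.2 and 11.10 and SAP 2.6.3 and 4.7, state whether the respiratory channels used for the baseline AHI are also recorded at Visits 4, 6 and 8.

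If they are:
- have the central laboratory already engaged for the study score AHI, and oxygen saturation if recorded, at Visits 2, 4, 6 and 8, blinded to arm;
- report in the Safety population the change from baseline by arm at each dose period, with a 95% CI for FT218 minus placebo;
- add a shift table around the protocol's own AHI limit of 15. Since subjects enter below 15, this is in effect a count by arm of those at or above 15 on treatment;
- give the number of subjects with a recording at each visit, because PSG after early withdrawal is discretionary (Protocol 8.3.4);
- label these outputs descriptive.

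If the channels are not recorded on treatment, or if redacted text already covers this, say so in the safety sections.

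The cost is a modest scoring fee and a few tables, with no added visit. The downside is a measure that varies from night to night and rests on one night per dose. No dose, treatment or stopping rule is proposed.

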10.1.2.4 Physical Examination

A complete physical examination including weight and evaluation of main body systems/regions, including: skin and mucous, ears/nose/throat, pulmonary, cardiac, GI, and neurological systems.

In case of abnormality, a comment will be recorded in the eCRF and subjects medical notes. Any deterioration in condition will be reported as an AE.

10.1.2.5 Electrocardiogram

Twelve-lead ECGs will be recorded after at least 5 minutes in the supine position.

Each ECG consists of a 10 second recording of the 12 leads simultaneously, leading to a 12-lead ECG (25 mm/s, 10mm/mV) printout with HR, PR, QRS, QT, QTc automatic correction evaluation, including date, time, initials and number of the subject, signature of the research physician, and at least 3 complexes for each lead. The ECG interpretation and values will be recorded in the eCRF.

10.1.3 Appropriateness of Measurements

The efficacy and safety assessments planned for this study are widely used and generally recognized as reliable, accurate, and relevant to the disease condition.

11 STATISTICAL METHODS

Two subject populations, one with both narcolepsy symptoms and one with EDS will be studied in a single parallel group dose-escalation design. The treatments are placebo and increasing doses of the test drug, FT218. Two primary outcome measures, MWT and CGI quantify the treatment effect on EDS and the NCA is the primary outcome measure for cataplexy.

[figure not shown]
11.1 Statistical and Analytical Plans

The material in this section provides the basis of the statistical analysis plan (SAP) for this study. A complete SAP has been prepared to accompany this protocol for submission to the FDA for the Special Protocol Assessment. Details are provided therein.

11.2 Definition of the Analysis Populations

The target population is individuals in need of treatment of EDS and cataplexy in subjects with narcolepsy. The full analysis population for efficacy is the intent-to-treat (ITT) population including all randomized subjects with at least one efficacy measurement after receiving the 6.0 g dose (whether FT218 or placebo).

11.2.1 Determination of Sample Size

Estimation of sample size to achieve a desired power depends on the number and nature of the hypothesis testing paradigm and assumptions about the magnitude of the underlying effects. In this study, hypothesis testing will proceed in the following order. First MWT and CGI will be examined for statistical significance in the full sample including both NT1 and NT2 subjects for the 9 g dose. If significant, NCA for the same dose will be tested in NT1 subjects. If the first test fails, the data from this dose is not able to reject the null hypothesis of equality to placebo. If the first test is significant, but the second fails, the dose has been demonstrated to be superior to placebo for EDS treatment, but not for cataplexy. If both tests are statistically significant, the dose has been shown to be effective for both EDS and cataplexy treatment. The same sequence of testing will be followed for the 7.5 g and then the 6.0 g dose in a hierarchical manner.

Each outcome measure for the 9.0 g, 7.5 g and 6.0 g dose will be tested at the 2-sided α level of 0.05.

